## 5.0 Inclusion and Exclusion Criteria/ Study Population

Participants will complete a REDCap survey to be screened for eligibility. Inclusion criteria for usability testing (Aim 1), feasibility testing (Aim 2), and the subsequent pilot RCT (Aim 3) include: 1) current elevated depressive symptoms defined as a score of  $\geq 10$  (at least mild depression) on the Patient Health Questionnaire-8 (PHQ-8); if a participant reports a Beck Depression Inventory-II (BDI-II) score  $< 10$  during baseline the PHQ from screening will be repeated with the participant over the phone (64), 2) current smoking, defined as smoking 5+ cigarettes/day, for 25+ days out of the last 30, for the last 6+ months, 3) ownership of an Android or iOS smartphone compatible with Goal2Quit, 4) age 18+, 5) a

valid e-mail address that is checked daily to access follow-up assessments, 6) English fluency, and 7) has been seen by a primary care physician within the last year. Exclusion criteria include: 1) contraindications for NRT (pregnancy/intention to become pregnant/breastfeeding, recent cardiovascular trauma/uncontrolled hypertension), 2) severe visual impairment, which may limit ability to utilize an app, and 3) household member currently enrolled in the study.

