**Assessments:** Assessments are estimated at 20 minutes each and will be administered remotely via REDCap through our established procedures. Participants will be sent an email and/or SMS text each week with a link to access their REDCap surveys. SMS text messaging is possible via Twilio, embedded within our RedCap system, which allows participants to complete a survey directly from their phone, without having to access a webpage. Note that surveys are not completed via texting, just prompted via text with link to RedCap. Participants can choose to receive their weekly surveys via email if they wish, again with a link to a secure RedCap survey. Participants will be compensated \$10 in cash and/or electronic gift codes (e.g., Amazon) for completion of each and will receive a \$20 bonus if at least 2/3 are complete. Participants will also receive a second bonus of \$20 for completing all follow up surveys. To help with retention, the last 20-25 participants enrolled will receive a signed letter from the study team and a few small items with the study’s logo (e.g., pen, flash drive, coaster, t-shirt) from the study team at random time points throughout their participation as a thank you for joining. Cigarette smoking, use of other tobacco products (e.g., e-cigarettes), and quit attempts/quit duration will be assessed at each follow-up using a timeline followback for the last 6-months at baseline and since prior follow-up for each subsequent assessment(71, 72). Nicotine dependence will be assessed at baseline via the Fagerstrom Test of Nicotine Dependence(73). Participants will report motivation to quit and confidence in quitting using a modified Contemplation Ladder(74). Depressive symptomatology will be assessed via both the PHQ-8(64) and the Beck Depression Inventory-II (BDI-II)(75). The PHQ-8 is briefer than the BDI-II, and thus will determine study eligibility. The BDI-II will be administered at all time points to determine change in symptoms. We will assess and track psychiatric medication use over time and will stratify randomization based on medication use. Adequate procedures are in place to assess for and protect against the potential for suicidal ideation (see Protection of Human Subjects). Process-related variables including activation, assessed via the activation subscale of the Behavioral Activation for Depression Scale(76), and environmental reward, assessed via the Reward Probability Index(77) will be assessed at baseline and all follow-ups to examine potential treatment mechanisms. Treatment adherence will reflect both Goal2Quit and NRT utilization. Regarding Goal2Quit, adherence will be measured based on 1) download of Goal2Quit (yes/no) and 2) analytic data including: number of logins, duration of sessions (average per session and cumulative), rolling retention, number of activities scheduled, and percent completed activities. Regarding NRT utilization, participants in both groups will be queried at all follow-ups for: 1) use of NRT since the last assessment, 2) purchase of NRT since the last assessment, and 3) perception of NRT products via the Attitudes Toward NRT Scale(78). Engagement in other cessation (other medications, behavioral treatment, quitlines) and mental health (medications, therapy) treatments will also be assessed. Feasibility and acceptability will be assessed for those in the Goal2Quit+NRT Sampling condition during each assessment. Participants will be prompted to

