
respond to questions querying their experiences with the intervention including: 1) ease of use, 2) barriers to utilization, and 3) suggested improvements to the treatment.

Measure	Screening	Baseline	1	2	3	4	5	6	7	8	12
PHQ-8	x										
BDI-II		x	x	x	x	x	x	x	x	x	x
Current use of Psychotropic Meds		x	x	x	x	x	x	x	x	x	x
Demographics	x	x									
Smoking History, Including History of Previous Quit Attempts and NRT Use		x									
BADS		x	x	x	x	x	x	x	x	x	x
RPI		x	x	x	x	x	x	x	x	x	x
SHAPS		x	x	x	x	x	x	x	x	x	x
SF-12		x				x					x
Tech Comfort		x									
Utilization of Goal2Quit /Other smoking cessation apps in the last week			x	x	x	x	x	x	x	x	x
Cigarettes per smoking day	x										
Fagerstrom Test of Nicotine Dependence		x									
TLFB (cigarettes, quit attempts, NRT)		x	x	x	x	x	x	x	x	x	x
Contemplation Ladder		x	x	x	x	x	x	x	x	x	x
MTQ Saliency		x	x	x	x	x	x	x	x	x	x
NRT Use			x	x	x	x	x	x	x	x	x
App Feedback (only for those who receive Goal2Quit)			x	x	x	x	x	x	x	x	x

Goal2Quit Usability Scale						x					
Attitudes Toward NRT		x	x	x	x	x	x	x	x	x	x
NRT AEs			x	x	x	x	x	x	x	x	x
Payment		\$10	\$10	\$10	\$10	\$10	\$10	\$10 +\$20 bonus (completing 6 out of 9 surveys)	\$10	\$10	\$10 + \$20 bonus (all surveys completed)

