## 11.0 Data Management

As this is a pilot trial, our primary goal is to determine feasibility/acceptability and estimate an intervention effect size. To estimate an effect size for the Goal2Quit+NRT Sampling intervention, we will randomize participants 2:1 (active:control), with 100 participants in the active condition and 50 in the control condition. Assuming a quit attempt rate (point prevalence) of 40% in the active condition and 15% in the control(59), with 2:1 randomization we will have 60% power to detect an effect; again our intent is not a fully powered trial. To further account for attrition (assumed to be 20% across groups), we will recruit 180 participants total. For this pilot RCT, with a 22-month enrollment period, subtracting three months for final study participants, we fully expect to feasibly recruit 9-10 participants per month (180 participants/19 months).

Data analysis will focus on descriptive analysis of changes over time in depressive symptoms and cigarette smoking by condition. Considering the relatively small sample, possible missing data, and repeated measures, we will fit the longitudinal data with Hierarchical Linear Modeling (HLM) to fully use available data(80). With HLM, we can estimate and model the degree of relatedness of our observations within the same treatment condition and within the same individual, thereby correctly estimating standard errors and eliminating the problem of inflated Type I error(81). First, we will assess patterns of missing data, research dropout, and distributional properties of all measures. Then, effects of the Goal2Quit+NRT Sampling intervention as compared to TAU on cigarette smoking (motivation to quit, confidence in quitting, and quit attempts/quit duration) and depressive symptoms over time will be examined using HLM. Planned covariates will include sex and baseline levels of depression and nicotine dependence as well as the main effect of time.

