### ***Data Management and Analysis***

Participants will enter data in REDCap, a secure, web-based application designed exclusively to support data capture for research studies. REDCap provides: 1) an intuitive interface for data entry (with data validation); 2) audit trails for tracking data manipulation and export procedures; 3) automated export procedures for seamless data downloads to common statistical packages (SPSS, SAS, Stata, R); 4) procedures for importing data from external sources; and 5) advanced features, such as branching logic and calculated fields. These procedures are effective in minimizing data entry errors (e.g., missing or errant data). The data analysis plan is outlined above.

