### ***Quality Assurance***

Accuracy and completeness of the data collected will be ensured by weekly review. The REDCap system does not accept outliers, illogical response patterns, etc. The PI and research assistants will have weekly meetings to discuss any qualitative comments received during data collection and any problems in data collection. The PI will examine the database for potential irregularities monthly. Initial data analyses will examine distributions of variable scores and comparability of baseline characteristics across conditions (for Aim 3) in case analyses need to be adjusted for these. Confidentiality procedures are outlined above.

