### Protections Against Risk

All screening information will be kept in a password protected REDCap database. Only key study personnel will have access to the database. If an individual is not eligible to participate, his/her screener will include his/her first name and last initial and the reason for disqualification. Eligible participants' full name, telephone number and e-mail address will be recorded in the database. This is the only place where participants' names and subject identification numbers appear together. Eligible participants will be assigned a subject number, will complete informed consent (see procedures above), will be randomized (Aim 3), will complete baseline assessments (Aims 2 and 3), and subsequently will receive their randomized intervention (or will complete usability testing for Aim 1).

Upon completing eligibility screening, if study eligible, individuals will be provided with an overview of the study, asked to review study procedures via a consent form, and asked to provide informed consent. Participants will be informed of limitations of confidentiality (i.e., abuse or neglect, intention to harm self or someone else) both verbally and/or in writing during the informed consent process. The consent form will include the participant's name, but not his/her subject number. Consent forms will be provided in English. As utilization of Goal2Quit requires that participants are able to read, participants unable to read the consent form on their own will not be included.

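### Randomisation is stratified by psychiatric-medication use, but the planned HLM covariates do not name that stratum, so standard errors for between-arm level contrasts may be slightly too large

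*Combined protocol and SAP*

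**What the plan says.** The Assessments paragraph of section 10.0 makes psychiatric-medication use a stratification factor: "We will assess and track psychiatric medication use over time and will stratify randomization based on medication use". The number of strata is not stated. The assessment schedule in the same section has a row "Current use of Psychotropic Meds", marked at baseline and at all nine follow-ups (weeks 1-8 and 12) but not at screening.

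Section 11.0 then lists the model terms: "Planned covariates will include sex and baseline levels of depression and nicotine dependence as well as the main effect of time". The Data Management and Analysis paragraph of section 12.0 adds nothing further: "The data analysis plan is outlined above". The only other provision for adjustment is under Quality Assurance in section 12.0, where initial analyses examine "comparability of baseline characteristics across conditions (for Aim 3) in case analyses need to be adjusted for these".

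Section 11.0 also gives the purpose of the pilot: "our primary goal is to determine feasibility/acceptability and estimate an intervention effect size".

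**The concern.** Stratified allocation makes the arms more alike on the stratifying factor than simple randomisation would. The true sampling variance of the treatment difference is then lower. A model without the stratum does not know this. It leaves the between-stratum variation in the residual and reports a standard error that reflects it. The usual remedy is to put in the model the factor used in the allocation.

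The Quality Assurance provision does not fill the gap. It is triggered by observed imbalance, and stratification is meant to prevent imbalance on exactly this factor.

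The outcomes concerned are the continuous ones: depressive symptoms, motivation to quit and confidence in quitting. What is at stake is the width of the interval around the effect size, and that estimate is part of the stated primary goal.

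**Working it through.** **Plan's own figure.** The plan gives none on this point. Its only power figure concerns quit attempts and is not an input here.

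**Inputs from the documents.** 2:1 allocation, 100 active and 50 control; nine follow-ups; 20% attrition; covariates and stratifier as above.

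**Assumptions, not in the documents.** R2, the share of residual between-person variance explained by the stratum after the planned covariates, is 2% to 10%. ICC, the between-person share of residual variance, is 0.4 to 0.8. The test is two-sided at 5%.

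**Formulas.** For a between-arm contrast averaged over m visits:

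- share of the contrast variance due to the stratum: s = R2 × ICC / (ICC + (1 − ICC)/m)
- SE inflation when the stratum is omitted: 1/√(1 − s)
- actual type I error: 2 × (1 − Φ(1.96/√(1 − s)))

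**Worked case.** R2 = 0.10, ICC = 0.6.

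- Single visit (m = 1): s = 0.06/(0.6 + 0.4) = 0.060; inflation 1/√0.940 = 1.031; type I error 0.0432.
- Mean of nine visits (m = 9): s = 0.06/(0.6 + 0.4/9) = 0.093; inflation 1/√0.907 = 1.050; type I error 0.0396.

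**Full range: SE inflation (type I error).**

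| m | ICC | R2 = 0.02 | R2 = 0.10 |
|---|---|---|---|
| 1 | 0.4 | 1.004 (0.0491) | 1.021 (0.0455) |
| 1 | 0.6 | 1.006 (0.0486) | 1.031 (0.0432) |
| 1 | 0.8 | 1.008 (0.0482) | 1.043 (0.0410) |
| 9 | 0.4 | 1.009 (0.0480) | 1.046 (0.0404) |
| 9 | 0.6 | 1.009 (0.0479) | 1.050 (0.0396) |
| 9 | 0.8 | 1.010 (0.0478) | 1.053 (0.0391) |

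With no within-person variance (ICC = 1) the limits are 1.010 (0.0477) and 1.054 (0.0388).

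**What this means for an interval.** With 100 and 50 observed, the reported 95% half-width is 1.96 × √(1/100 + 1/50) = 0.339 residual SD. At R2 = 0.10 and ICC = 0.8, the half-width with the stratum included would be 0.339 × √(1 − 0.080) = 0.326 SD for a single visit. For the nine-visit mean, in units of that mean's SD, it would be 0.339 × √(1 − 0.0973) = 0.323.

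**Simulation, single visit and nine-visit mean.** 20,000 null trials per setting; N = 150, 2:1, blocks of 6 in two strata of assumed equal prevalence, ICC 0.6. Results are for R2 = 0.02 and 0.10 in turn.

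- Single visit: SE ratio (omitted/included) 1.006 and 1.031; type I error omitted 0.0503 and 0.0415, included 0.0515 and 0.0471.
- Nine-visit mean: SE ratio 1.010 and 1.050; type I error omitted 0.0463 and 0.0411, included 0.0480 and 0.0510.
- The mean estimate without the stratum was within 0.001 of zero throughout. Monte Carlo error on the rejection rates is about 0.0015.

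**Simulation, repeated-measures model.** Random intercept, with arm, time and arm-by-time terms; nine visits; 20% monotone dropout; ICC 0.6; 8,000 trials at R2 = 0.02 and 10,000 at R2 = 0.10.

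- Arm term: SE ratio 1.009 and 1.050; type I error omitted 0.0499 and 0.0426, included 0.0523 and 0.0517.
- Arm-by-time term: SE ratio 1.0001 and 1.0004; type I error omitted 0.0449 and 0.0526, included 0.0456 and 0.0528.
- Monte Carlo error is about 0.002, so at R2 = 0.02 the conservatism cannot be told apart from noise.

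The simulated SE ratios agree with the formula to within 0.001.

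**The case against.** The case against acting has four parts.

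- **The list is open.** Section 11.0 says what the covariates will include and does not say that they are limited to those. A reader might infer that the sponsor decided to leave the stratum out. No text says so; the stratum is unnamed, not excluded. This stands, and the point is therefore one of incomplete specification.
- **The estimate barely moves.** The design has already balanced the factor and the model is linear, so the effect size carried to the larger trial is essentially the same either way. This stands. Only the reported precision is affected, and in the conservative direction.
- **The planned contrast may be condition-by-time.** Section 11.0 speaks of effects over time, and section 1.0 hypothesises greater decreases in depressive symptoms. If that is the contrast, omission costs almost nothing. This stands too, but section 11.0 does not name the contrast, so a level contrast remains possible.
- **The size is assumed.** Baseline depression is already a covariate and may absorb much of what medication use predicts. That is correct. Larger losses can be produced by assuming that the stratum explains 20-30% of outcome variance, but nothing in the documents supports such values and they should not be used to raise the severity.

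These objections limit the size of the point but do not remove it. Naming the stratum is free. It also prevents an analyst who later adds medication use from choosing the status recorded during follow-up, which is measured after randomisation and could be affected by treatment.

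**Conclusion.** The point holds and is minor. Followed as written, the plan omits its own stratification factor from the model. For level contrasts on continuous outcomes this inflates the standard error by about 0.4-4.3% at a single visit and 0.9-5.3% for the nine-visit mean. Type I error is then 4.9-4.1% and 4.8-3.9% respectively, instead of 5%. These ranges rest on the assumed R2 of 2-10% and ICC of 0.4-0.8. The condition-by-time result is for a random-intercept model. No claim is made for a logit model of quit attempts. No decision in this pilot changes.

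Two stronger readings are not supported. First, a reader might infer a biased effect size or too many false positives; the estimate is unbiased and any error is on the conservative side. Second, a reader might infer that participants are randomised before the stratifier is known, because Protections Against Risk in section 13.0 gives the order "will be randomized (Aim 3), will complete baseline assessments (Aims 2 and 3"). That sentence is a human-subjects narrative covering three aims. The Small-Scale RCT paragraph of section 10.0 is the explicit procedure and places randomisation after baseline assessments. The schedule agrees, since it first records medication use at baseline. So does section 5.0, where a low BDI-II score means that "during baseline the PHQ from screening will be repeated with the participant over the phone". The difference is editorial.

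**What to change.** Add to the covariates in section 11.0: *the baseline psychiatric-medication stratum, as used in randomisation*. The word *baseline* is needed because medication status is recorded again at every follow-up.

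The cost is wording only. The data are already collected, and the model gains one parameter if the stratum has two levels. Leave the Quality Assurance provision for baseline comparability as it stands; no harm from it has been shown.

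As an editorial side note, reconcile the order of randomisation and baseline assessments in section 13.0 with the Small-Scale RCT paragraph of section 10.0.

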## 11.0 Data Management

As this is a pilot trial, our primary goal is to determine feasibility/acceptability and estimate an intervention effect size. To estimate an effect size for the Goal2Quit+NRT Sampling intervention, we will randomize participants 2:1 (active:control), with 100 participants in the active condition and 50 in the control condition. Assuming a quit attempt rate (point prevalence) of 40% in the active condition and 15% in the control(59), with 2:1 randomization we will have 60% power to detect an effect; again our intent is not a fully powered trial. To further account for attrition (assumed to be 20% across groups), we will recruit 180 participants total. For this pilot RCT, with a 22-month enrollment period, subtracting three months for final study participants, we fully expect to feasibly recruit 9-10 participants per month (180 participants/19 months).

Data analysis will focus on descriptive analysis of changes over time in depressive symptoms and cigarette smoking by condition. Considering the relatively small sample, possible missing data, and repeated measures, we will fit the longitudinal data with Hierarchical Linear Modeling (HLM) to fully use available data(80). With HLM, we can estimate and model the degree of relatedness of our observations within the same treatment condition and within the same individual, thereby correctly estimating standard errors and eliminating the problem of inflated Type I error(81). First, we will assess patterns of missing data, research dropout, and distributional properties of all measures. Then, effects of the Goal2Quit+NRT Sampling intervention as compared to TAU on cigarette smoking (motivation to quit, confidence in quitting, and quit attempts/quit duration) and depressive symptoms over time will be examined using HLM. Planned covariates will include sex and baseline levels of depression and nicotine dependence as well as the main effect of time.

Regarding questionnaire data, data will be obtained for research purposes only. All data will be collected, stored, and managed via REDCap, which is a secure, web-based application designed exclusively to support data capture for research studies. REDCap provides secure, web-based flexible applications, including real time validation rules with automated data type and range checks at the time of entry. The underlying database is hosted in a secure data center at MUSC, a secure environment for data systems and servers on campus, and includes redundancy, failover capability, backups and extensive security checks. The system has several layers of protection including user/group account management, "Data Access Groups" which allow data to be entered by multiple groups in one database with segmented user rights for entered data, audit trails for all changes, queries and reports, and Secure Sockets Layer (SSL) encryption. Name and relevant contact information will be obtained to provide compensation and every effort will be made to maintain subject confidentiality, in accordance with HIPAA. All data will be identified only by code numbers (participant IDs). Participant IDs will be linked to participants' names in a password-protected file that is accessible only to the PI and trained research staff.

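### The stated 60% power does not follow from the plan's own inputs: 40% vs 15% with 100 and 50 participants gives about 90% at an assumed two-sided alpha of 0.05

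*Combined protocol and SAP*

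**What the plan says.** Everything needed except the significance level and the test stands in one paragraph of Section 11.0.

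- **Arm sizes:** "we will randomize participants 2:1 (active:control), with 100 participants in the active condition and 50 in the control condition".
- **Rates:** "Assuming a quit attempt rate (point prevalence) of 40% in the active condition and 15% in the control".
- **Power:** "with 2:1 randomization we will have 60% power to detect an effect; again our intent is not a fully powered trial".
- **Attrition:** "To further account for attrition (assumed to be 20% across groups), we will recruit 180 participants total".

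Attrition is thus added on top of the 150, so 100 and 50 read as the evaluable numbers. No alpha, sidedness or test is given for this comparison anywhere in the document. The only mention of Type I error concerns the hierarchical linear model, which is credited with "thereby correctly estimating standard errors and eliminating the problem of inflated Type I error"; no level is attached to it.

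**The concern.** A 25-point difference in proportions with 150 participants is a large effect for the sample, and 60% looks too low for it on sight.

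The figure matters because it is the only power statement for the RCT and it sits beside the remark that the trial is not meant to be fully powered. Quit attempts are among the hypothesised outcomes of Aim 3 (Section 1.0), and Section 10.0 describes the RCT as a test of efficacy. Someone who accepts 60% will think the design would miss a true difference of the assumed size four times in ten. If the usual 5% two-sided level is intended, the plan's inputs put that risk at about one in ten. A non-significant quit-attempt result would then be given less weight than the design warrants, in a study meant to inform a larger trial.

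**Working it through.** **Inputs (all Section 11.0).** p1 = 0.40, p2 = 0.15; n1 = 100, n2 = 50; attrition 20% with 180 recruited. **Assumed, not in the plan:** two-sided alpha 0.05 (z = 1.960) and a test of two proportions. Other alphas are shown below.

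**Attempt to reproduce 60% at 100:50, pooled z test.**

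- Power = Φ[(|p1 − p2| − z·SE0) / SE1]
- Pooled rate = (100 × 0.40 + 50 × 0.15) / 150 = 47.5 / 150 = 0.3167
- SE0 = √[0.3167 × 0.6833 × (1/100 + 1/50)] = 0.0806
- SE1 = √[0.40 × 0.60/100 + 0.15 × 0.85/50] = √0.00495 = 0.0704
- Power = Φ[(0.25 − 1.960 × 0.0806) / 0.0704] = Φ(1.31) = **90.5%**

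The stated 60% is not reproduced.

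**Other methods and the planned attrition.** 180 × 0.80 = 144, which at 2:1 is 96 and 48. Two-sided alpha 0.05:

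| Method | 100:50 | 96:48 |
|---|---|---|
| Pooled z | 90.5% | 89.2% |
| Unpooled z | 94.4% | 93.6% |
| Arcsine | 91.2% | 90.1% |
| Fisher exact (enumeration) | 89.2% | 87.7% |
| Continuity-corrected z | 86.3% | 84.6% |

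The continuity correction subtracts 0.5 × (1/n1 + 1/n2) from the difference. At 100:50 the gap from 60% is 26 to 34 points.

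**Other significance levels at 100:50 (pooled z).** One-sided 0.05: 95.3%. Two-sided 0.025: 83.8%. Two-sided 0.01: 72.7% (65.2% continuity-corrected).

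**Harshest reading consistent with the plan's numbers.** At 96:48, two-sided 0.01, continuity-corrected: Φ[(0.25 − 0.5 × (1/96 + 1/48) − 2.576 × 0.0822) / 0.0718] = Φ(0.31) = 62.3%. This combines an unstated strict alpha with the most conservative method, and it still does not fall to 60%.

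**What would give 60%?** These are pooled-z illustrations and shift with the method.

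- Half the sample, 50:25, at two-sided 0.05: 60.6% (Fisher exact 58.9%).
- 100:50 with a two-sided alpha of about 0.004 (about 0.007 with continuity correction).
- 100:50 at two-sided 0.05 with rates of about 40% vs 22%, or about 32% vs 15%.
- 80:40 (20% taken off the 150) at two-sided 0.01: 59.0%. At two-sided 0.05 the same 80:40 gives 82.5%, or 75.7% continuity-corrected.

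The document states none of these alphas or rates, and no 50:25 design. The 80:40 reading also conflicts with attrition being added on top of the 150.

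**The case against.** The strongest reply has three parts.

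1. **The 90% is conditional.** With no alpha, sidedness or test in the plan, 90% cannot be called the correct power. This stands, and it carries over to the one-in-ten risk of missing the effect: at two-sided 0.01 with continuity correction and 100:50, that risk is about 35%. What does not depend on the assumption is that the plan's stated inputs do not yield 60% and that no conventional level does so with 100 and 50 participants. The near match at 80:40 needs both an unstated alpha and a reading of attrition that the text contradicts.

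2. **The planned analysis is a hierarchical linear model, not a two-proportion test.** This is true, but the power sentence supplies only two rates and two arm sizes. There is no correlation, variance or number of time points from which power for a longitudinal model could be computed, so the model cannot account for the 60%.

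3. **It is a pilot.** The primary goal is feasibility, acceptability and an effect-size estimate; Section 1.0 expects differences that may be only numerical; and completed results should be read from the estimate and its confidence interval. This rightly limits the consequence. It justifies accepting low power but does not make an untraceable figure correct.

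**Conclusion.** The concern holds. With 40% vs 15% and 100:50, power is about 90% (86% to 94% by method) if a two-sided 0.05 test of two proportions is meant, and about 89% (85% to 94%) at 96:48 after the planned attrition. The stated 60% is roughly 30 points lower. Either the power, the rates or the arm sizes are wrong, or an undisclosed input was used; the document does not show which.

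The label in "Assuming a quit attempt rate (point prevalence) of 40% in the active condition and 15% in the control" adds to the uncertainty, because an attempt made over a period and a status at one time point are different measures, and the reader cannot tell which one the rates describe.

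The consequence is modest. The error understates power, and neither enrolment, allocation nor any decision rule depends on it. It is still worth correcting, as the only power figure for the RCT.

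**What to change.** In Section 11.0:

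- State the alpha, sidedness and test behind the quit-attempt power statement.
- If two-sided 0.05 is intended with the present rates, replace 60% with about 90% at 100:50 and about 89% at 96:48. If 60% is intended, give the rates, arm sizes or alpha that produce it.
- Keep the statement that this is a pilot for feasibility and effect-size estimation, but word it so that it does not imply low power for this comparison at these rates.
- Define the outcome to which the 40% and 15% refer, including its time window.

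This takes a few sentences and changes neither enrolment, allocation nor analysis.
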